*: No PBMC samples are taken for Revaccination Subcohort A.

Safety

With ~240 active study vaccine participants in Revaccination Subcohorts A and C, and ~270 active study vaccine participants in Revaccination Subcohort B, the observation of 0 events in the database would be associated with 95% confidence that the true rate is <1.5%.

The table below shows the probabilities of observing at least 1 AE in one of the arms at given true AE rates in the Revaccination Subcohorts.

True Adverse Event Rate	Revaccination Subcohorts A and C		Revaccination Subcohort B	
	Overall	Per Group	Overall	Per Group
	N=240 ^a	N=120 ^a	N=270 ^a	N=135 ^a
0.1%	21%	11%	24%	13%
0.5%	70%	45%	74%	49%
1%	91%	70%	93%	74%
2.5%	>99.9%	95%	100%	97%

^a Approximate number

Analysis Sets

- The Full Analysis Set (FAS) will include all randomized participants with a documented vaccine administration, regardless of the occurrence of protocol deviations. The FAS is the primary safety population. The analysis of solicited and unsolicited AEs after the Day 1 vaccination will be restricted to a subset of the FAS (ie, the Safety Subset).^a The analysis of solicited and unsolicited AEs after revaccination on Day 365 (Month 12)/Day 730 (Month 24)/Day 1,095 (Month 36) will be restricted to participants of the Revaccination Subcohorts that are part of the FAS.
- The Per-protocol Immunogenicity (PPI) population will include all randomized and vaccinated participants for whom immunogenicity data are available. Samples taken after a participant experienced a major protocol deviation expecting to impact the immunogenicity outcomes will be excluded from the PPI. The analysis of immunogenicity will focus on 2 subsets of the PPI, ie, the Immuno Subset and the Revaccination Subcohorts.

In addition, for participants who experience a natural RSV infection (based on RT-PCR, or other sources), samples taken after the natural infection will not be taken into account in the assessment of the immunogenicity.

The PPI population is the primary immunogenicity population. For key tables, sensitivity immunogenicity analyses will also be performed on the FAS, including participants for whom immunogenicity measures are available. Excluded samples might be taken into account as well in the sensitivity analysis.

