Revaccination Subcohorts A, and C will each consist of approximately 120 participants from Group 1 who received active study vaccine on Day 1 and approximately 120 participants from Group 2 who received placebo on Day 1, and who have given informed consent for the additional study procedures. Revaccination Subcohort B will consist of at least 135 participants from Group 1 who received active study vaccine on Day 1 and at least 135 participants from Group 2 who received placebo on Day 1, and who have given informed consent for the additional study procedures. Participants in the Revaccination Subcohorts will receive a revaccination with active study vaccine at 1, 2, or 3 years after the first vaccination, as shown in [Table 2](#). The enrollment of Revaccination Subcohorts A and C will stop when both groups have reached at least 120 participants. The enrollment of Revaccination Subcohorts B will stop when both groups have reached at least 135 participants.

Participants in Revaccination Subcohorts 2A and 2B will be re-randomized to Ad26.RSV.preF/RSV preF protein mixture or the individual vaccine components in a 1:1:1 ratio in a blinded manner.

Blinding

The investigator will not be provided with randomization codes. The codes will be maintained within the IWRS, which has the functionality to allow the investigator to break the blind for an individual participant.

In general, randomization codes will be disclosed fully only if the study is completed and the clinical database is closed. The study participants, study-site personnel (except for those with primary responsibility for study vaccine preparation and dispensing), and investigator will be blinded to study vaccine allocation throughout the study. The sponsor will be blinded to study vaccine allocation until the database lock for the primary analysis. Site staff and participants will remain blinded until the end of the study.

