11.2.3. Safety Subset

While mild to moderate vaccine reactions (local injection site, systemic responses) are expected, AEs that preclude further vaccine administration (if applicable) are not anticipated.

With ~350 active study vaccine participants in the Safety Subset, the observation of 0 events in the database would be associated with 95% confidence that the true rate is less than 1%. For SAEs, which will be captured in all participants, the observation of 0 events in the database would be associated with 95% confidence that the true rate is less than 0.1%.

In addition, a cap will be installed to ensure that 350 participants in the Safety Subset (~175 in each group) are at increased risk for severe RSV disease. With 175 active study vaccine

participants at increased risk of severe RSV disease in the Safety Subset, the observation of 0 events (solicited or unsolicited) in the database would be associated with 95% confidence that the true rate in participants at increased risk of severe RSV disease is less than 1.7%.

SAEs will be captured in all participants. Outside the Safety Subset and Immuno Subset, no cap is installed on the number of participants at increased risk of severe RSV disease. It is expected that participants at increased risk for severe RSV disease will represent approximately 30% of the overall population. Assuming that 30% of the participants in the overall population are at increased risk of severe RSV disease (~870 participants), the observation of 0 events in participants at increased risk of severe RSV disease would be associated with 95% confidence that the true rate is less than 0.4%.

Table 7 shows the probabilities of observing at least one AE in one of the arms at given true AE rates in the Safety Subset (overall population and participants at increased risk of severe RSV disease).

Table 7: Probability of Observing at Least One Adverse Event or Serious Adverse Event at a Given True Adverse Event Rate in the Safety Subset

True Adverse Event Rate	Probability of Observing at Least One Adverse Event in N Participants			
	Overall N=350	Overall N=2,900	Increased Risk N=175	Increased Risk N=870 ^a
0.1%	30%	95%	16%	58%
0.5%	83%	100%	58%	99%
1%	97%	100%	83%	100%
2.5%	>99.9%	100%	99%	100%

^a Approximate number

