Table 9 shows the actual distance from the mean to the limits of 95% CI around the Day 15 post second vaccination ratio between the 2 groups, for the different assays. The calculations consider an exclusion rate of 10% from the sample size of revaccinated participants (~108 participants per group for Revaccination Subcohorts A and C, and ~120 participants per group for Revaccination Subcohort B).

Table 9: Distance From the Mean to the Limits of 95% CI Around the Ratio on Day 15 Post Second Vaccination Between the 2 Groups for Pre-F ELISA, VNA A2, and ELISpot

Revaccination Subcohort	Assay	N (per group)	Distance ^a from Mean to Limits 95% CI	95% CI if Observed Ratio is 1
A and C	Pre-F ELISA (SD=1.3)	120	0.349	(0.79;1.27)
	VNA (SD=1.5)	120	0.402	(0.76;1.32)
	ELISpot (SD=1.2)*	50	0.476	(0.72; 1.39)
B	Pre-F ELISA (SD=1.3)	135	0.331	(0.79;1.26)
	VNA A2 (SD=1.5)	135	0.381	(0.77; 1.30)
	ELISpot (SD=1.2)	135	0.305	(0.81; 1.24)

CI = confidence interval, ELISA = enzyme-linked immunosorbent assay, ELISpot = enzyme-linked immunospot (assay), SD = standard deviation, VNA = virus neutralization assay

^a Calculated on the log₂-scale.

*: No PBMC samples are taken for Revaccination Subcohort A.

Safety

With ~240 active study vaccine participants in Revaccination Subcohorts A and C, and ~270 active study vaccine participants in Revaccination Subcohort B, the observation of 0 events in the database would be associated with 95% confidence that the true rate is <1.5%.

Table 10 shows the probabilities of observing at least 1 AE in one of the arms at given true AE rates in the Revaccination Subcohorts.

Table 10: Probability of Observing at Least 1 Adverse Event or Serious Adverse Event at a Given True Adverse Event Rate in the Revaccination Subcohorts

True Adverse Event Rate	Revaccination Subcohorts A and C		Revaccination Subcohort B	
	Overall	Per Group	Overall	Per Group
	N=240 ^a	N=120 ^a	N=270 ^a	N=135 ^a
0.1%	21%	11%	24%	13%
0.5%	70%	45%	74%	49%
1%	91%	70%	93%	74%
2.5%	>99.9%	95%	100%	97%

^a Approximate number

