11.11. Safety Analyses

No formal statistical testing of safety data is planned. Safety data by vaccination group and based on the FAS will be analyzed descriptively. The analysis of solicited and unsolicited AEs will be restricted to a subset of the FAS (ie, the Safety Subset). For SAEs, the complete FAS is considered. The impact of baseline factors (eg, being at increased risk for severe RSV disease) might be explored as well. Additionally, the analysis of solicited and unsolicited AEs and AESIs (if collected) will also be performed for each of the Revaccination Subcohorts and will be restricted to participants of the Revaccination Subcohorts that are part of the FAS.

Adverse Events (Solicited and Unsolicited)

The verbatim terms used in the eCRF by investigators to report AEs will be coded using the Medical Dictionary for Regulatory Activities (MedDRA). All reported AEs with onset during the active vaccination phase (ie, AEs occurring after vaccination up to 28 days post-vaccination), and all SAEs and AESIs will be included in the analysis. For each AE, the number and percentage of participants who experience at least 1 occurrence of the given event will be summarized by group.

Solicited local (at the injection site) and systemic AEs will be summarized descriptively. The overall frequencies per group as well as frequencies according to severity and duration will be calculated for solicited AEs.

Summaries, listings, datasets, or participant narratives may be provided, as appropriate, for those participants who die, who discontinue the study (or study vaccination, if applicable) due to an AE, or who experience a severe AE, an SAE, or an AESI.

Any ARI recorded as an (S)AE in the eCRF will be excluded from any AE analysis if the laboratory RT-PCR is subsequently found to be positive for RSV. ARIs arising from RSV infection will not be reported as (S)AEs in the Clinical Study Report as they are endpoints of the study and will be tabulated separately.

Vital Signs

A tabulation of the distribution of temperatures in the 7 days after vaccination, per half degree intervals, will be provided. For systolic and diastolic blood pressures, pulse rate and respiratory rate, the percentage of participants with values beyond clinically relevant limits will be summarized.

Physical Examination

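### Two stated safety-precision figures are slightly better than the design delivers: the >99.9% cell in Table 10 (exact value 99.8%) and the <0.1% bound for SAEs (0.103% to 0.109%)

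*Protocol*

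**What the plan says.** Section 11.2.3 (Safety Subset) gives zero-event bounds: below 1% for about 350 active participants, below 1.7% for 175 at increased risk, and below 0.4% for about 870 at increased risk. On SAEs it says "For SAEs, which will be captured in all participants, the observation of 0 events in the database would be associated with 95% confidence", and names 0.1% as the limit. Table 7 uses N=2,900 as the per-arm number for SAEs. Section 11.2.1 sets 2,750 per group if the study stays in the Northern Hemisphere, with a further 150 per group if it extends to the Southern.

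Section 11.2.4 does the same for revaccination: "With ~240 active study vaccine participants in Revaccination Subcohorts A and C, and ~270 active study vaccine participants in Revaccination Subcohort B, the observation of" no events is tied to a limit of 1.5%, again at 95% confidence. Table 10 then "shows the probabilities of observing at least 1 AE in one of the arms at given true AE rates in the Revaccination Subcohorts", with Overall columns (N=240, N=270) and Per Group columns (N=120, N=135). Its entry for a 2.5% rate with N=240 is >99.9%.

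The synopsis repeats both zero-event statements and both tables. On the make-up of the totals, Section 5 says "Revaccination Subcohorts A, and C will each consist of approximately 120 participants from Group 1 who received active study vaccine on Day 1" and the same number from the placebo group; Subcohort B has at least 135 from each. Section 11.11 says "Safety data by vaccination group and based on the FAS will be analyzed descriptively" and that the analysis is repeated for each Revaccination Subcohort.

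**The concern.** These statements tell a reader which event rates a clean safety database could rule out. An upper bound or detection probability printed more favourably than the design supports errs in the unsafe direction, even by a small amount. The SAE bound is a strict inequality at a round value (1 in 1,000) that may be quoted on its own. The Table 10 cell is also a strict inequality, so ordinary rounding does not excuse it.

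The revaccination sentence raises a separate question of clarity. Its totals add participants whose revaccination dose is their second active dose to participants who had placebo on Day 1 and are receiving active vaccine for the first time. Someone interested in repeat dosing needs the smaller group's precision, and the sentence does not give it.

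**Working it through.** **Inputs.** N = 350, 175, 870, 2,900 and 2,750 (Sections 11.2.1 and 11.2.3, Table 7); N = 240, 270, 120 and 135 (Section 11.2.4, Table 10).

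**Formulas.** Upper 95% bound after zero events: 1 − 0.05^(1/N). Chance of at least one event at true rate r: 1 − (1 − r)^N.

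**Which convention the protocol uses.** The one-sided bound reproduces its other figures:

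| N | One-sided bound | Protocol states |
|---|---|---|
| 350 | 0.852% | <1% |
| 175 | 1.697% | <1.7% |
| 870 | 0.344% | <0.4% |
| 240 | 1.240% | <1.5% |
| 270 | 1.103% | <1.5% |

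A two-sided limit, 1 − 0.025^(1/N), gives 2.086% at N=175 and 1.048% at N=350, which would contradict the text. The convention is therefore one-sided.

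**SAE bound.**
- N=2,900: 1 − 0.05^(1/2,900) = 0.103%.
- N=2,750: 1 − 0.05^(1/2,750) = 0.109%.
- N needed for 0.1%: ln(0.05)/ln(0.999) = 2,994.2, so 2,995 active recipients. The plan is 95 short in the two-hemisphere design and 245 short in the Northern-Hemisphere-only design.
- Cross-check with Table 7: at a 0.1% rate and N=2,900, 1 − 0.999^2,900 = 94.5%, printed as 95%. A bound of 0.1% would need at least 95%.

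**Table 10, rate 2.5%.**
- N=240: 1 − 0.975^240 = 99.77%, printed as >99.9%.
- N=270: 99.89%, printed as 100%, which is correct to the nearest whole per cent.
- N=120: 95.21%, printed as 95%. N=135: 96.72%, printed as 97%.
- N needed to exceed 99.9%: ln(0.001)/ln(0.975) = 272.8, so 273. Neither 240 nor 270 reaches it.

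The other Table 10 rows reproduce. At 1%, for example, the values are 91.0%, 70.1%, 93.4% and 74.3% against printed 91%, 70%, 93% and 74%.

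**Per-group bounds for revaccination.** N=120 gives 2.47% and N=135 gives 2.20%. Table 10 already implies this: a 95% chance of at least one event at a 2.5% rate with N=120 is the same statement as zero events excluding about 2.5%.

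**The case against.** The fair reply is that both discrepancies are trivial: 0.103% is 0.1% to one decimal, 99.77% is a near-certainty like 99.9%, and safety is descriptive, so nothing is decided on either number. The point about consequence stands. The rounding defence does not, because both entries are written as strict inequalities and an upper bound rounded downwards claims more than was shown.

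A second reply is that SAEs are captured in both arms, which would give 5,800 participants and a bound of 1 − 0.05^(1/5,800) = 0.052%. But half of those received placebo, the preceding sentence in Section 11.2.3 counts active participants, and Table 7 works with 2,900 in one arm.

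A reader might go further and infer that the <1.5% bound is itself an arithmetic error because it pools first and second active doses. The protocol does not support that. Both groups receive active vaccine at revaccination, the sentence names the totals it uses, the bound is true and slightly conservative for them, and the Per Group columns directly below carry the smaller-group precision. Two further inferences also fail:

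- That no planned summary will use 240 or 270. Section 11.11 summarises by group but also provides for an analysis of each subcohort, and whether tables carry a total column is a matter for the SAP.
- That the placebo-first half adds nothing. AESIs are collected only after revaccination, so in Subcohorts B and C those participants supply the AESI data after a first active dose.

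Nor is there ground to predict that a clean result in the twice-vaccinated group would be reported as excluding 1.5%; the text attaches that figure to the pooled totals.

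**Conclusion.** Two figures are wrong as written. The Table 10 cell for a 2.5% rate and N=240 should be 99.8%, in Section 11.2.4 and in the synopsis. The SAE bound below 0.1% is not reached: it is 0.103% with 2,900 active recipients and 0.109% with 2,750. Both errors are small and favour the design; neither affects sample size, conduct or any planned analysis.

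The <1.5% statement is correct for 240 and 270. What it lacks is a label. Only the active-first half (about 120 in A and in C, about 135 in B) informs a second active dose, and for that half zero events excludes about 2.5% or 2.2%.

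The conclusion assumes the one-sided exact convention, which the protocol's other bounds confirm, the planned group sizes with no loss, and that the SAE bound refers to active recipients.

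**What to change.** 1. In Table 10 and the matching synopsis table, replace >99.9% at a 2.5% rate with N=240 by 99.8%.
2. In Section 11.2.3 and the synopsis, restate the zero-SAE bound as <0.11%, which holds for both 2,750 and 2,900 active recipients.
3. Optional: in Section 11.2.4 and the synopsis, say that the totals of 240 and 270 combine participants receiving their first and their second active dose, add the per-group bounds (about 2.5% for 120 in A and C, about 2.2% for 135 in B), and note that only the active-first half informs a second active dose.

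The cost is a text correction in two places for each item. The corrected figures are slightly less favourable than those printed, and nothing else in the plan changes.

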11.3. Participant Information

For all participants in the FAS, demographic characteristics (eg, age, height, weight, BMI, race, and gender), and other baseline characteristics (eg, physical examination findings, medical history, and concomitant diseases) will be tabulated and summarized with descriptive statistics. Important tables might be repeated for other analysis sets.

11.4. Efficacy Analyses

11.4.1. Primary Efficacy Endpoints

Three primary efficacy endpoints are defined as follows:

- First occurrence of RT-PCR-confirmed RSV-mediated LRTD according to Case Definition #1
- First occurrence of RT-PCR-confirmed RSV-mediated LRTD according to Case Definition #2
- First occurrence of RT-PCR-confirmed RSV-mediated LRTD according to Case Definition #3

The case definitions are defined as follows:

Case Definition #1	Case Definition #2	Case Definition #3
≥3 symptoms of LRTI (new onset or worsening)	≥2 symptoms of LRTI (new onset or worsening)	≥2 symptoms of LRTI, OR ≥1 symptom of LRTI combined with ≥1 systemic symptom
		(new onset or worsening)

LRTI = lower respiratory tract infection

To meet the primary endpoint according to the respective case definitions the following criteria will be taken into account:

- symptoms reported by participants on the RiiQ Symptom Scale and body temperature during the full ARI episode OR
- clinical assessment terms reported by a qualified study staff member during the ARI Days 3-5 clinical visit

in combination with

- confirmation of RSV by RT-PCR in one or more of the midturbinate nasal swabs, or in the sputum sample (when available)

Of note, on the day of the ARI Days 3-5 clinical visit, the case definitions can be met by symptoms reported by participants on the RiiQ or by signs and symptoms reported by the qualified study staff member. Case definitions cannot be met by a combination of symptoms reported by the participant with signs and symptoms reported by the qualified study staff member.

Confirmation of RSV infection by RT-PCR (midturbinate swabs and sputum sample, when available) will be performed at the central laboratory. For participants hospitalized with symptoms of an ARI, confirmation of RSV infection using an FDA-approved RT-PCR test at the local (hospital) laboratory will also be used for the analysis of case definitions if results from the central laboratory are not available. One positive sample (defined as any sample with a value above the limit of detection) is sufficient.

As a sensitivity analysis, the analysis of the primary endpoint will be repeated, but participants with RSV infection and a co-infection with at least one other respiratory virus (ie, confirmed using an FDA approved RT-PCR test in one or more of the midturbinate nasal swabs, or in the sputum sample, when available) will not be considered as a case for that episode, as the etiology of the symptoms will be indeterminate.

As an additional sensitivity analysis, the analysis of the primary endpoint will be repeated, taking into account only the RT-PCR test results from the central laboratory (ie, excluding the local test results for hospitalized participants).

Presence and severity of symptoms will be collected using participant responses to the RiiQ Symptom Scale and temperature readings participants report in the eDiary each day throughout each ARI episode. On the day of the ARI Days 3-5 clinical visit, signs and symptoms will also be collected by qualified study staff in a clinical assessment.

Table 11: Symptoms of Lower Respiratory Tract Infection and Systemic Symptoms as per RiiQ or Clinical Assessment

	Symptoms from Case Definition	RiiQ Term	Clinical Assessment Term (ARI Days 3-5 Clinical Visit)
Symptoms of LRTI	Cough	Cough	Cough
	Shortness of breath	Short of breath	Dyspnea or decreased oxygen saturation*
	Sputum production	Coughing up phlegm (sputum)	Sputum production
	Wheezing	Wheezing	Wheezing; rhonchi, rales or other sign of consolidation
Systemic Symptoms	Tachypnea**		Tachypnea
	Fatigue	Fatigue (tiredness)	Malaise (tiredness)
	Fever***,****		Fever
	Feverishness****	Feeling feverish	

* Decreased oxygen saturation is defined as oxygen saturation of <90% for participants with a baseline oxygen saturation of $\geq 90\%$ at randomization; for participants with baseline oxygen saturation <90%, decreased oxygen saturation is defined as a $\geq 3\%$ decrease in their oxygen saturation from baseline.

** Tachypnea is defined as respiratory rate >20 breaths per minute.

*** Fever (ie, temperature >37.8°C) will be reported via daily temperature measurement and during ARI Days 3-5 clinical visit.

**** Feeling feverish and fever are considered as 1 symptom.

LRTI =lower respiratory tract infection, RiiQ = Respiratory Infection Intensity and Impact Questionnaire

Symptoms (new onset or worsening) occurring at the same day will be counted. When during ARI Days 3-5, symptoms are reported more than once per day by the participant (eg, on the site's eDevice and in the participant eDiary), the worst severity from the RiiQ will be taken into account. On the day of the ARI Days 3-5 clinical visit, signs and symptoms collected during the clinical assessment by a qualified study staff member will be considered separately from the symptoms reported by the participant on the site's eDevice or in the participant eDiary. A new onset of a symptom is a symptom that is reported during the ARI episode and that was not reported at baseline (defined by pre-dose assessment on the day of vaccination for the first RSV season, the Day 365 [Month 12] visit for the second RSV season [pre-vaccination if applicable], and at the Day 730 [Month 24] visit for the third RSV season). Worsening of a symptom is defined as a symptom that is reported at baseline (defined by pre-dose assessment on the day of vaccination for the first RSV season, at the Day 365 visit for the second RSV season [pre-vaccination if applicable], and at the Day 730 visit for the third RSV season) that worsens in severity during the ARI episode compared to baseline.

First occurrence of a considered endpoint is defined as the first episode of the considered endpoint in a given RSV season (regardless A or B strain, unless otherwise specified).

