9.2.1.4. Clinical Assessment

At baseline, and between 2 and 4 days after symptom onset (ARI Days 3-5) and at ARI Day 29, a study staff member will perform a clinical assessment ([Attachment 3](#)):

- Vital signs: body temperature, systolic and diastolic blood pressure, heart rate, respiratory rate, and oxygen saturation measurement.
- Symptom collection and targeted physical examination: cough, sputum production, shortness of breath, and malaise (tiredness)
- Upper respiratory: nasal discharge, pharyngitis, and sinus tenderness
- Lower respiratory: dyspnea, rales, rhonchi or other, wheezing, and respiratory effort

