Attachment 3: Clinical Assessment

CLINICAL QUESTIONNAIRE	
Participant ID:	

VITAL SIGNS	
Temperature (°C/°F)	
Blood pressure (SBP/DBP)	
Heart rate (bpm)	
Respiratory rate (breaths per minute)	
Oxygen saturation (SpO ₂)	

PHYSICAL EXAMINATION SCORING				
Level	0	1	2	3
	No Symptoms	Just noticeable	Bothersome sometimes, not interfering with other activities	Bothersome most of the time, interfering with other activities
Cough				
Sputum production				
Shortness of breath				
Malaise (tiredness)				

UPPER RESPIRATORY				
Level	0	1	2	3
Nasal Discharge	None	Clear, serous: scant but slightly increased	Clear to white, obvious increased volume, + minor blood streaks on tissue	Frankly purulent (yellow or green), or gross blood
Pharyngitis	None	Mild and/or patchy erythema	Marked and/or confluent erythema	Erythema and purulent exudate
Sinus Tenderness	None		Mild tenderness	Severe tenderness or overlying erythema

LOWER RESPIRATORY				
Level	0	1	2	3
Dyspnea	None	May have brief episodes	May have increased episodes	May have severe episodes
Rales, rhonchi or other	None		Scattered wheezes or rhonchi	Widespread wheezes or rhonchi, rales, dyspnea, or signs of consolidation
Wheezing	None	Terminal expiration or only with stethoscope	Entire expiration or audible on expiration without stethoscope	Inspiration and expiration without stethoscope
Respiratory Effort	None	Mild chest wall retraction	Trachea tug with moderate chest wall retraction and nasal flare	Marked chest wall retraction with nasal flare

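### Table 11 does not count the staff-scored shortness-of-breath item toward the case-definition symptom of the same name, so the staff route to the primary endpoints can miss an episode, though probably rarely

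*Protocol*

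**What the plan says.** Section 11.4.1 gives two routes to each case definition, both requiring RT-PCR confirmation. The participant route uses "symptoms reported by participants on the RiiQ Symptom Scale and body temperature during the full ARI episode OR"; the staff route uses "clinical assessment terms reported by a qualified study staff member during the ARI Days 3-5 clinical visit". The two may not be pooled: "Case definitions cannot be met by a combination of symptoms reported by the participant with signs and symptoms reported by the qualified study staff member".

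Table 11 translates each case-definition symptom into a RiiQ term and a staff term. For shortness of breath, the RiiQ item on being short of breath counts for the participant. The staff column reads "Dyspnea or decreased oxygen saturation". Its footnote defines decreased saturation as below 90% when baseline was at least 90%, or a fall of at least 3% when baseline was lower. For cough, sputum production and fatigue, the staff column names the form items cough, sputum production and malaise.

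Section 9.2.1.4 puts the staff findings in separate groups. One is "Symptom collection and targeted physical examination: cough, sputum production, shortness of breath, and malaise (tiredness"; another is "Lower respiratory: dyspnea, rales, rhonchi or other, wheezing, and respiratory effort". Attachment 3 keeps them apart. It has a row labelled "Shortness of breath", scored 0 to 3 by how noticeable and bothersome the symptom is. Dyspnea has a different row, scored by episodes, whose level 1 reads "May have brief episodes".

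**The concern.** The form has one staff item with exactly the name of the case-definition symptom, and Table 11 leaves out that item. The Protocol gives no reason. Read literally, staff can record new shortness of breath in an RSV-positive participant and the algorithm will not count it. The participant's report of the same symptom does count, so the two routes apply different content under one symptom name.

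The algorithm feeds all three primary endpoints. The season 2 and season 3 endpoints inherit it (Section 11.4.3), and the ordinal definition in Table 12 rests on the same symptom count. Section 1.2 says the trial should help select a case definition for Phase 3, so an unexplained gap could carry forward. If some readers take the dyspnea term to cover both rows and others do not, two programmers could derive different case counts from the same data.

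**Working it through.** **Step 1. Set the symptom block against Table 11.**

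| Staff item (9.2.1.4, Attachment 3) | Named in Table 11, staff column? |
|---|---|
| Cough | Yes |
| Sputum production | Yes |
| Malaise | Yes (for fatigue) |
| Shortness of breath | No; dyspnea or decreased saturation instead |

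Three of four are mapped by name. The fourth is not.

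**Step 2. Score three hypothetical records.** Each is RSV-positive, seen at the ARI Days 3-5 visit, with every item 0 at baseline, dyspnea 0, SpO2 95% and no other listed finding.

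| Record | Count under Table 11 | Count if the item is added | Definition that changes on the staff route |
|---|---|---|---|
| Cough 1, shortness of breath 2 | 1 LRTI | 2 LRTI | #2 (needs 2); #3 as well |
| Cough 1, sputum 1, shortness of breath 1 | 2 LRTI | 3 LRTI | #1 (needs 3) |
| Shortness of breath 2, malaise 1 | 0 LRTI, 1 systemic | 1 LRTI, 1 systemic | #3 |

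**Step 3. Ask when such a record is a lost case.** All of the following must hold:

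- Staff score shortness of breath as new or worse, and dyspnea at 0 (more generally, not new or worse).
- Saturation does not meet the footnote's rule.
- The participant's RiiQ record does not meet the definition on any day of the episode.

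The third condition is demanding. The RiiQ runs daily. It is also completed on the site's device at the Days 3-5 visit (Section 9.1.1), asks for the worst of the past 24 hours (Attachment 5), and takes the worst same-day severity (Section 11.4.1). In the first record, a participant who reports new cough and shortness of breath on the same day meets #2 without any staff finding.

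**Step 4. Context for size.** Section 11.2.1 expects 26 Case Definition #2 cases. Its inputs are placebo incidence 0.75%, VE 70% and 10% exclusions, so expected cases = participants per group × 0.9 × 0.0075 × (1 + 0.30).

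- 2,900 per group: 2,610 × 0.00975 = 25.4.
- 2,750 per group: 2,475 × 0.00975 = 24.1.

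Both are close to the stated 26. No input gives the share of cases meeting the conditions in Step 3.

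For scale only, power was computed for 2,475 per group at one-sided 0.05 without multiplicity correction. The method was an exact conditional binomial test on a Poisson total, with vaccine share 0.30/1.30 under the alternative. The proportions lost are assumptions, taken as equal in both arms.

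| Assumed loss | 0% | 2% | 5% | 10% | 20% |
|---|---|---|---|---|---|
| Power | 81.7% | 80.9% | 79.7% | 77.4% | 72.3% |

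The zero-loss value agrees with the stated 80%. Nothing in the Protocol says where in this range, if anywhere, the trial lies.

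**The case against.** Dyspnea is the clinical word for shortness of breath, so the symptom is mapped. The column lists terms, not form fields, and which field feeds a term could be left to the statistical analysis plan, as Section 11 allows for specific details. Not every collected item has to count: respiratory effort is unmapped too. The RiiQ is a complete alternative route. A record with bothersome shortness of breath but no dyspnea at the same visit is discordant and should be uncommon.

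The points about the RiiQ and discordance stand, and they limit the size. The synonym argument does not settle the mapping. Attachment 3 makes dyspnea its own row with its own anchors, and where Table 11 wants several findings to count for one symptom it lists them, as it does for wheezing with rhonchi and rales. Respiratory effort is a weaker parallel, because no case-definition symptom bears its name.

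A further objection concerns timing. This version is Amendment 8, dated 16 February 2023. All three Northern Hemisphere ARI cut-offs (20 March 2020, 17 May 2021, 15 April 2022) precede it, and Section 5 ends the sponsor's blind at the primary-analysis lock. Widening a primary case definition after unblinding would be post hoc. That stands, and it shapes the fix.

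**Conclusion.** The mismatch is in the text: a staff-recorded shortness of breath does not count as the symptom of that name, and an RSV-positive episode can fail a case definition on the staff route because of it. The loss is probably small, since every condition in Step 3 must hold. It should not differ between arms, since staff score without knowing the allocation. The likely cost is a few events and some power. The Protocol gives no discordance rate, so no number of lost cases should be claimed.

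A reader might infer that the omission could decide proof of concept. For example, a 7:18 split of vaccine to placebo cases gives a one-sided exact binomial p of 0.0216 and 7:19 gives 0.0145, on either side of 0.0175. The documents do not support that use. The 0.0175 comes from an interim illustration in Section 11.4.1.1 with 14, 18 and 25 events, and the actual cut-off depends on observed counts. The planned test is a stratified exact Poisson regression using follow-up time. The example also assumes that the missing case is on placebo; a missing vaccine case would move p the other way. A reader might also infer a biased VE estimate, but nothing in the Protocol points to differential loss.

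**What to change.** In Table 11, staff column, shortness-of-breath row, write: shortness of breath, dyspnea, or decreased oxygen saturation. Count these together as one symptom, and judge new onset or worsening on each item's own baseline. Carry the same rule into the season 2 and 3 endpoints where their derivation is still blinded.

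For any season already unblinded, keep the derivation that was used as primary and report a sensitivity analysis that counts the item. Run it for every season, so that comparisons across seasons use one rule.

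The item is already collected at the baseline visits and at ARI Days 3-5, so the cost is one table cell, one line of derivation code and, where needed, one extra analysis. The downside is that a few more mild episodes would qualify by the staff route.
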